4.3. Accrual

We expect to accrue a minimum of 24 evaluable patients (plus up to 12 replacements for patients removed from the study prior to completion of the assigned vaccine schedule for any reason other than toxicity). The study may require 30-42 patients if DLT occur that necessitate re-dosing at a lower dosage levels (see section 6 for a description of the dose escalation criteria).

4.4 Assignment of study number: Patients will be assigned study numbers in order of their screening using the following: ETBX-011-xxx.

- Assignment of study day: Day 0 is the day of the first immunization. The second immunization is at Day 21.

5. PRE-TREATMENT EVALUATION

(See also Schema in Appendix 1.) The following pre-treatment evaluations will be completed within 1 month (+/- 2 weeks) before starting study treatment:

- History and physical exam, to include ECOG Performance Score and review of inclusion and exclusion criteria
- β -HCG for women with childbearing potential
- Hematological, biochemical and immunological tests:
 - CBC with differential
 - PT INR and PTT
 - Na, K, Cl, CO₂, BUN, creatinine, Ca, total protein, albumin, total bilirubin, alkaline phosphatase, AST, ALT and glucose
 - Urinalysis
- Infectious Disease
 - HIV antibody, Hepatitis BsAg, Hepatitis C serology, CMV serology
- ECG
- Biological Markers:
 - Serum will be obtained to measure antibodies to CEA and the neutralizing antibodies to Ad vector, and other available serum markers (e.g., CEA or CA15-3) will be reviewed.
- Archive Samples:
 - An additional 20 mL of blood may be drawn during the first clinic visit, when the patient history and physical exam are conducted, at the discretion of the immune monitoring laboratory, and serum stored for later analysis of immune responses.
- Imaging studies:
 - CT or MRI scans of the chest, abdomen, brain, and/or pelvis will be requested within 1 month (± 2 weeks) before starting study treatment to document the presence and size of any measurable metastatic disease that might present. CT and MRI are the best currently available and reproducible methods to measure target lesions selected for response assessment. Conventional CT and MRI should be performed with cuts of 10 mm or less in slice thickness contiguously. Spiral CT should be performed using a 5 mm contiguous reconstruction algorithm. This applies to tumors in the chest, abdomen, and pelvis.

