- 4.2.8. Patients on steroid therapy (or other immuno-suppressives, such as azathioprine or cyclosporin A) are excluded on the basis of potential immune suppression. Patients must have had 6 weeks of discontinuation of any steroid therapy (except that used as pre-medication for chemotherapy or contrast-enhanced studies) prior to enrollment.
- 4.2.9. Patients with allergies to any component of the vaccine will be excluded from the protocol.
- 4.2.10. Pregnant and nursing women should be excluded from the protocol since this research may have unknown and harmful effects on an unborn child or on young children. If the patient is sexually active, the patient must agree to use a medically acceptable form of birth control while receiving treatment and for a period of 4 months following the last vaccination therapy. It is not known whether the treatment used in this study could affect the sperm and could potentially harm a child that may be fathered while on this study.
- 4.2.11. Patients with acute or chronic skin disorders that will interfere with injection into the skin of the extremities or subsequent assessment of potential skin reactions will be excluded.
- 4.2.12. Patients will be allowed warfarin 1mg po qd for port prophylaxis but not full dose warfarin or low molecular weight heparin.

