5. Reporting Adverse Events: An adverse experience is any adverse change from the study patient's baseline (pre-treatment) condition, including any clinical or laboratory test abnormality that occurs during the course of the proposed clinical study after treatment has started. All adverse experiences that are classified as serious as described in section 10.7 of the protocol should be reported to the sponsor (Etubics) by telephone or fax within 24 hours, and reported in writing to the sponsor (etubics) within 72 hours. All study-related deaths should be reported to the IRB within 24 hours; all other serious adverse experiences should be reported to the IRB within 5 business days. All deaths, whether considered study-related or not, must also be reported immediately to the principal investigator, with a copy of the autopsy report and the death certificate. All adverse experiences will be recorded on the Adverse Experience Case Report Form. This report form should include severity, duration, outcome, and the investigator's judgment as to the relationship of the adverse experience to treatment.
6. Reporting of Pregnancy: If a participant becomes pregnant during the study, treatment will be discontinued (*i.e.*, no additional dose of study vaccine will be given) and the participant will be encouraged to continue to have regularly scheduled follow-up visits and evaluations. The occurrence of pregnancy, and the outcome of any pregnancy, in a subject treated with study vaccine, must be reported to the sponsor (Etubics), and to the IRB.

10.6. CTCAE Term (AE description) and Grade:

The descriptions and grading scales found in the revised NCI Common Terminology Criteria for Adverse Events (CTCAE) version 4.0 will be utilized for AE reporting. All appropriate treatment areas should have access to a copy of the CTCAE version 4.0. A copy of the CTCAE version 4.0 can be downloaded from the CTEP web site (<http://ctep.cancer.gov>).

The CTCAE displays Grades 1 through 5 with unique clinical descriptions of severity for each AE based on the following guideline:

Grade 1	Mild AE
Grade 2	Moderate AE
Grade 3	Severe AE
Grade 4	Life-threatening or disabling AE
Grade 5	Death related to AE

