4.2. Criteria for Patient Exclusion

- 4.2.1 Patients with concurrent cytotoxic chemotherapy or radiation therapy should be excluded. There are no exclusions based on the number of prior chemotherapy, biologic, hormonal, or experimental regimens. Except for the permitted concomitant therapies (bevacizumab, cetuximab, panitumumab, trastuzumab, lapatinib, erlotinib, gefitinib, or hormonal therapy which patients must have been on for at least 3 months at the time of enrollment if they intend to continue them with the vaccine), there must be at least 3 months between any prior CEA-targeted immunotherapy and study treatment and at least 4 weeks between any other prior therapy (including radiotherapy) and study treatment. Patients must have recovered to grade 1 acute toxicities from prior treatment.
- 4.2.2. Patients with a history of or current brain metastases will not be permitted.
- 4.2.3. Patients with a history of autoimmune disease, such as but not restricted to, inflammatory bowel disease, systemic lupus erythematosus, ankylosing spondylitis, scleroderma, or multiple sclerosis. Autoimmune related thyroid disease and vitiligo are permitted.
- 4.2.4. Patients with serious intercurrent chronic or acute illness, such as cardiac disease (NYHA class III or IV), hepatic disease, or other illness considered by the Principal Investigator as unwarranted high risk for investigational drug treatment.
- 4.2.5. Patients with a medical or psychological impediment to probable compliance with the protocol should be excluded.
- 4.2.6. Concurrent (or within the last 5 years) second malignancy other than non-melanoma skin cancer, cervical carcinoma *in situ*, controlled superficial bladder cancer, or other carcinoma *in situ* that has been treated.
- 4.2.7. Presence of an active acute or chronic infection including: a urinary tract infection, HIV (as determined by ELISA and confirmed by Western Blot). Patients with HIV are excluded based on immuno-suppression, which may render them unable to respond to the vaccine; patients with chronic hepatitis are excluded because of concern that hepatitis could be exacerbated by the injections.

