7. TREATMENT EVALUATION

7.1. Short-Term Evaluation During and After Active Immunotherapy

On vaccine administration days, blood will be drawn before administration. Evaluations will also be conducted for patients who discontinue from the study if they have received any treatment. The investigator will determine the degree of evaluation based on the patient's condition and/or reason for discontinuation from the study.

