12. APPENDIX 1 – SCHEMA

Procedure / Test	Pre-treatment	Week 0	Week 3	Week 6	Week 9	Months 6, 9, etc. ⁱ	Off Treatment
H & P	X	X	X	X	X	X	X
Karnofsky Status	X	X	X	X	X	X	X
β-HCG ^a	X						
CBC with diff	X	X	X	X	X	X	X
PT-INR, PTT	X						
Chemistries	X	X	X	X	X	X	X
Urinalysis	X						
ANA	X				X		X
HIV	X						
Immune Monitoring ^b	X ^b	X	X	X	X	X ^b	X ^b
Antibodies to CEA/Ad5 Vector ^c		X			X		
Biological Markers ^d (i.e. CEA, CA15-3)	X ^d				X ^d	X ^d	X ^d
Brain MRI/CT Scan ^e	X						
MRI/CT Scan ^f	X ^f				X ^f	X ^f	X ^f
Immunization ^g		X	X	X			
AE Assessment ^h	X	X	X	X	X		

Key: H & P = history & physical examination, KPS = Karnofsky Performance Score, β-HCG = human chorionic gonadotrophin pregnancy test; CBC & diff = complete blood count and white blood cell differential, Chemistries = Na, K, Cl, CO₂, BUN, creatinine, Ca, total protein, albumin, total bilirubin, alkaline phosphatase, AST, ALT and glucose; ANA = antinuclear antibody, HIV = human immunodeficiency virus antibody, MRI/CT = magnetic resonance imaging/computed tomography; AE = Adverse Event

Notes:

- ^a β-HCG performed on women of childbearing potential
- ^b Immune monitoring drawn during the first clinic visit at the discretion of the investigator/immune monitoring laboratory, prior to each immunization and approximately 3 weeks after the last immunization, and will be repeated at the discretion of the investigator/immune monitoring laboratory.
- ^c Serum obtained for antibodies to CEA and Ad5 vector weeks 0 and 9.
- ^d Available serum markers (e.g., CEA or CA15-3) reviewed as available.
- ^e Brain CT scan or MRI required within 6 weeks of starting study treatment.
- ^f Available CT scans or MRI of the chest, abdomen, and/or pelvis reviewed. Imaging studies within 6 weeks of starting study treatment is preferred, however is not required. Repeat imaging conducted according to standard of care.
- ^g Immunizations may be modified so that the interval is between 20 and 28 days (3 weeks -1 day to 3 weeks +7 days). If the second and/or third immunization is delayed, the subsequent immunizations should occur no earlier than 20 days after the previous immunization.
- ^h AE monitoring from the time of informed consent to 30 days after the last dose of study drug.
- ⁱ Follow-up evaluations requested every 3 months for 1 year, while on the study.

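### The only scheduled pregnancy test may be about 6 weeks old at dose 1 and over a year old at cohort 6 boosters, and the protocol does not say which pre-dose sample settles eligibility or serves as the toxicity baseline

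*Combined protocol and SAP*

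**What the plan says.** The combined document holds seven protocol versions. This point rests on the latest, the one that adds cohort 6; the screening window reads the same in all seven.

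- **Window.** Section 5: "The following pre-treatment evaluations will be completed within 1 month (+/- 2 weeks) before starting study treatment". The list includes the "review of inclusion and exclusion criteria", β-HCG, CBC, PT/INR/PTT and chemistries.
- **Pregnancy.** Exclusion 4.2.9: "Pregnant and nursing women should be excluded from the protocol since this research may have unknown and harmful effects on an unborn child". Appendix 1, note a: "β-HCG performed on women of childbearing potential". The row has one mark, under Pre-treatment. Sexually active patients must also agree to contraception during treatment and for 4 months after the last vaccination.
- **Prior therapy.** Exclusion 4.2.1 requires "at least 4 weeks between any other prior therapy (including radiotherapy) and study treatment", with stated exceptions, and recovery of acute toxicities from prior treatment to grade 1.
- **Week 0.** Section 7.1: "On vaccine administration days, blood will be drawn before administration". Sections 7.1.1 and 7.1.2 and Appendix 1 repeat history, physical examination, Karnofsky status, CBC and chemistries at that visit.
- **Toxicity baseline.** Section 10.5 defines an adverse event as an adverse change from the patient's "baseline (pre-treatment) condition, including any clinical or laboratory test abnormality that occurs during the course of the proposed clinical study after treatment has started". That is the spelling in the earliest version; the latest has the same definition with the word unhyphenated.
- **DLT.** In Section 6 of the latest version, the Grade 3 or higher non-hematologic item carries no wording on attribution or new onset. The fever item does mention a possible link to immunization.

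**The concern.** An exclusion protects patients only if the information behind it is reasonably current when vaccine is given. Pregnancy is excluded because of possible harm to the unborn child, yet the schema tests once, before a course lasting 6 to 8 weeks for most cohorts and more than a year for cohort 6. The coagulation limits in 4.1.7 are in the same position: the latest version admits patients on warfarin with an INR below 3, and INR is not scheduled again.

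For CBC and chemistries a fresh pre-dose value exists, but the protocol gives it no role. It does not say whether eligibility is judged on the screening or the Week 0 sample, or against which of the two a later value is graded as change. Six-patient cohorts tolerate one DLT, so an ambiguity about what was present before dosing touches the quantity that determines the MTD.

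**Working it through.** The plan states no figure on this point to reproduce. The check is date arithmetic plus a comparison of sections.

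**1. Age of screening tests at dose 1.** Upper limit = 1 month + 2 weeks. With a month of 28, 30 or 31 days: 28 + 14 = 42, 30 + 14 = 44, 31 + 14 = 45 days, or 6.0 to 6.4 weeks. Section 5 separately uses 6 weeks for brain imaging, which fits this reading.

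**2. Age of the pregnancy test at dose 3.** Section 6 sets 3-week intervals, extendable to 28 days. Dose 3 falls on day 2 × 21 = 42, or at latest day 2 × 28 = 56. Test age: 42 + 42 = 84 days on schedule, 42 + 56 = 98 days at the limit (87 and 101 with a 31-day month).

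**3. Age at cohort 6 boosters.** Boosters run every 3 months after the first three doses, for one year according to the Protocol Summary and two years according to Section 6, item 6. Assuming a booster at the end of the period:
- one year: 42 + 42 + 365 = 449 days;
- two years: 42 + 42 + 730 = 814 days.

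Even a test done on the day of dose 1 would be 42 + 365 = 407 days old at a one-year booster. The two durations conflict and need reconciling; the conclusion is the same under either.

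**4. What is repeated before injection (Appendix 1, latest version).**

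| Item | Criterion | Pre-treatment | Week 0 | Weeks 3, 6 |
|---|---|---|---|---|
| β-HCG | 4.2.9 | yes | no | no |
| PT-INR, PTT | 4.1.7 | yes | no | no |
| CBC | 4.1.7 | yes | yes | yes |
| Chemistries | 4.1.8 | yes | yes | yes |
| Karnofsky | 4.1.4 | yes | yes | yes |

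The schema also has no immunization mark beyond Week 6, so the boosters do not appear in it.

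**5. Overlap with prior therapy.** 42 − 28 = 14 days: screening laboratory values may predate the last permitted cytotoxic dose by up to 2 weeks. The Week 0 draw falls after that interval, but no readable section ties its results to 4.1.7 or 4.1.8.

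**6. Baseline.** Appendix 1 lists Pre-treatment and Week 0 as separate columns. Section 10.5 uses the pretreatment condition as baseline, and a Week 0 pre-injection value is also pretreatment. The text fits either. Section 10.5 also monitors adverse events from consent while defining them as arising after treatment has started.

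**7. Size of a possible miscount.** The documents give no rate, so this is illustration only. Assume a true DLT rate of 10% and an independent per-patient miscount probability m. Then p = 1 − 0.9(1 − m), and P(2 or more of 6) = 1 − (1 − p)^6 − 6p(1 − p)^5.

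| m | p | P(2 or more of 6) |
|---|---|---|
| 0 | 0.100 | 11.4% |
| 1% | 0.109 | 13.2% |
| 2% | 0.118 | 15.1% |
| 5% | 0.145 | 21.2% |

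**The case against.** A reader might infer that abnormalities present before dosing will be counted as vaccine toxicity and could settle the MTD. The documents do not support that:
- The adverse event definition requires onset after treatment has started.
- CBC, chemistries, performance status, history and physical examination are repeated at Week 0, with blood drawn before injection.
- Adverse event assessment starts at consent, so pre-dose events can be recorded as such.
- Section 10.7 weighs timing and underlying conditions in judging causality, and Section 8.1 gives the escalation decision to the medical monitor and the principal investigator.
- No section says that baseline is the screening value.

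A calculation that takes one carried-over event in a cohort as certain would show a much larger shift than step 7, but it assumes the thing in question.

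It would also be wrong to say that all eligibility tests are stale at dose 1, or that prior-chemotherapy toxicity is ignored: 4.2.1 requires recovery to grade 1. That clause does not cover disease-related change or pregnancy.

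On pregnancy, the contraception agreement and the repeated history offer some protection. The agreement does not name the time between screening and dose 1, and neither detects a pregnancy. Part of the later text on pregnancy reporting is missing from the public copy, so nothing is inferred from its absence.

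The single β-HCG mark, the single coagulation test, the unassigned role of the Week 0 results and the unspecified baseline remain.

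**Conclusion.** The point holds in limited form. Followed as written, the latest version allows vaccination of a woman whose only scheduled pregnancy test is about 42 days old at dose 1, 84 to 98 days old at dose 3, and more than a year old at late boosters. These ages assume the full screening window is used and, for boosters, that one is given at the end of the stated period. PT-INR and PTT likewise have no scheduled value after screening.

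The undefined baseline, together with a non-hematologic DLT item that lacks attribution or new-onset wording, makes a miscount possible but not directed. Its frequency is unknown. The illustrative figures in step 7 depend on an assumed rate and should not drive the priority. The case for change rests on the pregnancy test and the unstated eligibility sample, and on how little correcting them costs.

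**What to change.** 1. Reconcile the single β-HCG mark in Section 5 and Appendix 1 with exclusion 4.2.9 and the dosing schedule: add β-HCG marks, for women of childbearing potential, on the blood already drawn before each immunization. Show the cohort 6 boosters in the schema so that the marks can cover them.
2. In Section 10.5, define the toxicity baseline as the last value before the first injection.
3. Reconcile Section 5, criteria 4.1.7 and 4.1.8 and the Week 0 draw, so that the protocol states which sample the eligibility limits apply to. Cover PT-INR/PTT, which has no Week 0 value.

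How an out-of-range result is handled clinically is for the sponsor and investigators to state; no rule is proposed here.

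Cost: a few pregnancy tests and an occasional screen failure at Week 0. Items 1 and 2 add no visit or venipuncture, because blood is already drawn on every vaccination day.

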6. TREATMENT PLAN

In the phase I component, patients will be enrolled into successive dosage level cohorts of 3 or 6 patients and monitored for dose-limiting toxicity (DLT).

DLT (based on CTCAE4.0 criteria) is defined as any Grade 2, 3 or 4 immediate hypersensitivity reactions, other Grade 3 or 4 allergic or major organ toxicity, or Grade 4 fever that may possibly be associated with the immunization.

During dose escalation through the first three patients of cohort 3, there will be a minimum of 1 week between enrolling successive patients. If no DLT have been observed at this point, then further enrollment can occur in cohort 3 and phase II component without the 1-week waiting period. Between dosage levels, assessment of DLT for dose escalation will be made after all patients in a cohort have had a study visit at least 3 weeks after receiving their first dose of vaccine and all the available safety data and laboratory results have been reviewed by the Principle Investigator. If DLT occurs in <33% of patients in a given dosage level cohort, progression to the next dosage level will proceed. If DLT occurs in $\geq 33\%$ of patients in a given cohort, the next lower dosage level will be defined as the maximum tolerated dose (MTD). If DLT occurs in <33% of patients in the highest dosage level tested, that dosage level will be defined as the MTD. In phase II, 12 additional patients will be enrolled at the MTD. In phase II, if at any time the rate of DLT in patients enrolled at the MTD (for the phase I and phase II cohorts combined) is $\geq 33\%$, the MTD will be re-defined as the next lower dosage level, and phase II will proceed with enrollment of additional patients at this lower dosage level. Additional details of this dose escalation and de-escalation plan are provided below and in Figures 3A, 3B and Table 3.

- 1) Phase I: Cohort 1: Three patients will receive Ad5 [E1-, E2B-]-CEA(6D) at a dose of 1×10^9 particles in 0.5 mL subcutaneously (SQ) in the same thigh every 3 weeks for 3 immunizations. Immunizations should be separated by 5 cm. Assessment of DLT for dose escalation will be made after all patients in this cohort have had a study visit at least 3 weeks after receiving their first dose of vaccine. If there are no DLT (as defined above), then patients may begin enrolling into cohort 2. If there is 1 DLT then an additional 3 patients will be enrolled at this dosage level. Assessment of DLT for dose escalation will be made after the 3 additional patients have had a study visit at least 3 weeks after receiving their first dose of vaccine. If none of these latter 3 patients have DLT, then patients may begin enrolling into cohort 2. If 2 patients have DLT at this lowest dosage level, dosing will be suspended and the study re-evaluated.
- 2) Cohort 2: Three patients will receive Ad5 [E1-, E2B-]-CEA(6D) at a dose of 1×10^{10} particles in 0.5 mL SQ in the same thigh every 3 weeks for 3 immunizations. Assessment of DLT for dose escalation will be made after all patients in this cohort have had a study visit at least 3 weeks after receiving their first dose of vaccine. If there are no DLT, then patients may begin enrolling into cohort 3. If there is 1 DLT then an additional 3 patients will be enrolled at this dosage level. Assessment of DLT for dose escalation will be made after the 3 additional patients have had a study visit at least 3 weeks after receiving their first dose of vaccine. If none of these latter 3 patients have DLT, then patients may begin enrolling into cohort 3. If 2 patients have DLT at this dosage level, the dosage level in cohort 1 will be considered the MTD. If only 3 patients were enrolled in cohort 1, an additional 3 patients will be enrolled at that dosage before proceeding to phase II.
- 3) Cohort 3: Six patients will receive Ad5 [E1-, E2B-]-CEA(6D) at a dose of 1×10^{11} particles in 0.7 mL SQ in the same thigh every 3 weeks for 3 immunizations.

Assessment of DLT for proceeding to phase II enrollment will be made after all patients in this cohort have had a study visit at least 3 weeks after receiving their first dose of vaccine. If there is 0 or 1 DLT, then this dosage level will be considered the MTD and patients may begin enrolling into the phase II portion of the study. If 2 patients have DLT at this dosage level, the dosage level in cohort 2 will be considered the MTD. If only 3 patients were enrolled in cohort 2, an additional 3 patients will be enrolled at that dosage before proceeding to phase II.

- 4) Phase II cohort: After the MTD is established, an additional 12 patients will receive Ad5 [E1-, E2B-]-CEA(6D) at the MTD every 3 weeks for 3 immunizations.

Note: if during accrual of patients in the phase II cohort, DLT occurs at a sufficient rate such that the rate of DLT amongst the total number of patients (those treated at MTD in phase I and those in phase II) is $\geq 33\%$, then phase II will be restarted at the dosage level which is one level below the prior MTD.

- 5) Patients will have 90 mL peripheral blood drawn prior to each immunization and approximately 3 weeks after the third immunization (Week 9) to determine whether there is an effect on the immune response at specific time points during the study and/or after a specific number of immunizations.
- 6) Time to progression will be measured using CT scans performed at approximately 3 month intervals (based on clinical standard of care).
- 7) For all patients, if scheduling conflicts arise, the scheduled 3-week interval between immunizations may be modified so that the interval between immunizations is between 20 and 28 days (3 weeks -1 day to 3 weeks +7 days). If the second and/or third immunization is delayed, the subsequent immunizations should occur no earlier than 20 days after the previous immunization.
- 9) The following safety events will trigger a temporary suspension of study vaccinations:
 - a) If $\geq 66\%$ of patients in cohort 1 experience DLT
 - b) If $\geq 33\%$ of patients in the phase II cohort experience DLT at dosage level 1 (i.e., 1×10^9 particles)
 - c) If one or more patients develop a Grade 4 allergic reaction without a clear attributable cause, other than study vaccine
 - d) If, at any time, more than 50% of patients experience a Grade 3 or 4 major organ toxicity
 - e) Death not attributed to disease.

Assessment of these halting rules is a review of cumulative events for all study participants, and should not be confused with reasons for delaying or terminating the immunization schedule of any individual patient.

The Scientific Monitoring Subcommittee of the Cancer Protocol Committee (CPC) will fully review all available safety data, consult with the principal investigator, medical

monitor and the FDA as needed, before determining if resuming vaccinations is appropriate. If it is determined that study vaccinations can resume, the halting rules will apply to each subsequent event that meets the criteria described above.

Vaccinations may also be suspended for safety concerns other than those described above if, in the judgment of the principal investigator or sponsor, participant safety is threatened.

Figure 3A

[figure not shown]

Figure 3B.

[figure not shown]

Table 3. Calculation of rates of DLT during patient accrual in phase I and phase II

# evaluable for toxicity	1,2,3	4,5,6	7,8,9	10,11,12	13,14,15	16,17,18
# with DLT to be ≥33%	1	2	3	4	5	6

